TITLE

A randomized trial of vaginal prep solutions to reduce bacteria colony counts in patients having a vaginal surgery.

INVESTIGATORS

[name], [name], [name]

SUMMARY OR ABSTRACT

This is a randomized trial comparing the effectiveness of 4 vaginal prep solutions (betadine, baby shampoo, TechniCare and Peridex) on reducing bacterial colony counts during surgery preparation. Women undergoing a vaginal surgery will be enrolled into the trial prior to surgery. Target sample size per group is 15 patients. During standard surgical prep, a vaginal swab will be taken to assess the initial colony counts for aerobic and anaerobic bacteria. After the initial swab, the vagina will be prepared using one of the prep 4 solutions (betadine, baby shampoo, TechniCare or Peridex). After a predefined 10 minutes, the area will be re-swabbed to determine pre-procedure colony counts. A third swab will be taken following completion of the procedure to determine post-procedure colony counts. Laboratory analyses for raw colony counts, sensitivities, identification (using MALDI-TOF) will be performed. We expect that there will be reduced colony counts at the pre-procedure point with baby shampoo having the least reduction, followed by betadine and TechniCare, then Peridex. Patient reported outcomes for vaginal itching and burning as well as patient report of any treatment for vaginal infection will be collected by telephone at 2 days, 2 weeks and 1 month post-surgery.

BACKGROUND AND LITERATURE REVIEW

Antiseptic preparation for surgical incision sites has greatly reduced postoperative infections. However, surgical site infections (SSI) are still the leading cause of hospitalizations after

surgery. With the application of antiseptic preparation, a reduction in bacterial counts follows.

The rate at which the bacterial counts rise between preparation and incision may be of variation depending on the surgical antiseptic scrub.

Betadine (Povidone- iodine), Peridex (Chlorhexidine), baby shampoo and TechniCare (chloroxyne) are all surgical scrubs approved for the preparation of vaginal access surgeries.

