While there has been controversy on the use of Chlorohexidine for vaginal preparation surgery, due to its labeling as a cause for irritation, studies have shown that when 2-4% Chlorhexidine is used in the vaginal area there are little to no signs of irritation and the bacteria counts post incision are less than the bacterial counts for povidone iodine^{1,2}. Baby shampoo can also be used as an effective antiseptic scrub with no irritation and no statistical difference in bacterial count reduction as compared to povidone-iodine³. Little research has been done to look at the antiseptic power of Chloroxylenol in vaginal surgeries. However, when used as a root canal antiseptic it can reduce bacteria counts by 99.9%⁴. This is illustrative of its capability to reduce bacteria on a mucus membrane similar to the vagina.

There is literature that shows the antiseptic power of Betadine, Peridex, Baby shampoo and TechniCare for post-incisional bacteria counts, but little is known about the pre-incisional power of these scrubs for vaginal access surgeries.

SPECIFIC AIMS OR OBJECTIVES

The aim of this study is to understand the power of vaginal surgical scrubs before and after procedure completion. This will be done by collecting bacterial samples before antiseptic preparation, 10 minutes after antiseptic preparation, and after completion of the procedure along with follow-up data of irritation, infection post-surgery, and infection risk factors of each patient.

SIGNIFICANCE TO PATIENT, INSTITUTION, PROFESSION, OR ALL

Vaginal preparation research provides beneficial knowledge to hospitals and physicians in the prevention of surgical site infections (SSI). This specific project will provide insight regarding the bacteria-eliminating power of four different surgical scrubs used on the vaginal mucous membrane. There is potential for this study to determine the most effective scrub for vaginal surgeries, as well as correlate pre-procedure bacterial counts and likelihood of surgical site infections. The information collected from this study could benefit future patients and hospitals alike in terms of reducing the risk of SSI's. The risks of this study could be unidentified allergies to any of the surgical scrubs, or a loss of patient data. These are unlikely risks due to the protocol of the study.

METHODS

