Each patient will be given a standard prophylaxis 30 minutes before surgery. After prophylaxis administration and before surgical antiseptic preparation, a 10 second swab will be taken of the vagina making sure to span the surface area of the vaginal canal with avoidance of the cervix. The swab will then be broken off into a tube labeled with the patient ID, date, and “pre-scrub.” The patient will then undergo antiseptic preparation with the assigned surgical prep. A standard procedure of application will be done for each of the arms. Ten minutes after application, another swab will be taken using the same procedure as the “pre-scrub” swab. This swab will be broken off in a tube labeled with the patient ID, date, and “post-scrub.”¹ Following the conclusion of the procedure, a third swab will be taken using the same procedure as the two pre-incision swabs. The third swab will then be broken off into a tube labeled with the patient ID, date, and “post-procedure-swab.” The swabs will then be transported to CompuNet where they will be analyzed for aerobic, anaerobic bacteria and fungal colonies using Matrix Assisted Depolarization/Ionization Time of Flight mass spectrometry (MALDI-TOF).

The data of colony counts will be collected from CompuNet. BMI, age, prophylaxis, postmenopausal information, diabetic information, smoking history, surgical duration, complication in surgery, and length of hospital stay will all be collected from patient records. No patient identifiers will be collected⁵. Patients will be followed up on their surgery approximately two days, two weeks and a month after surgery to get information on irritation and/or surgical infection. This data will be collected either be phone call or at post-surgical follow-up appointment at Wright State Physicians. The South Hampton Grading Scheme for Surgical

Wounds will be used to Quantify Each patients level of irritation and/or infection. The scale is a Zero to Five score, with Zero being no irritation or infection and Five being severe irritation or infection¹⁵.

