One potential obstacle of this study could be recruitment of patients. Patients will not be given incentive for participation and will not acquire any direct benefit from the study. Another potential issue may arise from the size of the study; there may not be enough subjects recruited for each arm of the study to find a detectable and significant difference in the use of one surgical scrub over another. There may also not be sufficient power to detect a difference in the risk of post-operative surgical site infections.

Precautions will need to be taken for allergies. A recruited patient may not be aware of personal allergies to the surgical scrubs. This would put the patient in harm if they are assigned to a scrub that they are allergic to. Since data will be collected from the patient's medical records, precautions will be taken to avoid loss of patient identifiers. All research investigators will only utilize the patients assigned research ID. This will both protect the patient and avoid bias.

Statistical Analysis Plan

Bacterial and fungal colony counts will be coded as positive if counts are ≥ 5000 colonies/mL

and negative if < 5000 colonies. Statistical analyses will be conducted as follows:

Baseline characteristics will be compared with Chi square (categorical data) and ANOVA (continuous data) to determine potential differences for demographic and clinical characteristics and for colony counts (positive vs negative) at the pre-scrub sample collection.

Each of the 3 target scrubs (baby shampoo, chlorhexidine and chloroxyne) will be compared to povidone-iodine as the standard of care using Fisher's Exact tests for each pair comparison at the

post-scrub and post-procedure collections.

REFERENCES

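### The trial asks how far each scrub lowers colony counts, but the SAP compares arms only on positivity at 5000; no analysis of the size of the reduction is planned, and power is lost at 15 per arm

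*Combined protocol and SAP*

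**What the plan says.** The Summary states its hypothesis on the scale of the reduction: "We expect that there will be reduced colony counts at the pre-procedure point with baby shampoo having the least reduction". Relative to povidone-iodine, the standard-of-care comparator in the SAP, this and the rest of the ranking in the same sentence predict a smaller reduction with baby shampoo, a similar one with TechniCare and a larger one with Peridex. The Significance section likewise speaks of the "bacteria-eliminating power of four different surgical scrubs".

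The data are to be counts. The Summary says "Laboratory analyses for raw colony counts, sensitivities, identification (using MALDI-TOF) will be performed", and Methods says "The data of colony counts will be collected from CompuNet", with swabs before the scrub, ten minutes after it and after the procedure.

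The Statistical Analysis Plan opens with the cut: "Bacterial and fungal colony counts will be coded as positive if counts are ≥ 5000 colonies/mL". Each of the other three scrubs is then compared with povidone-iodine by Fisher's exact test at the post-scrub and post-procedure swabs. The pre-scrub count appears once, in the baseline comparison, again as a binary: "for colony counts (positive vs negative) at the pre-scrub sample collection". The SAP describes no mean or log count, no change from the pre-scrub swab and no baseline adjustment. It gives no reason for the 5000 cut, no alpha and no multiplicity rule.

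**The concern.** A hypothesis about how far counts fall is to be tested with an endpoint that records only which side of one threshold a patient ends on. A patient who falls from 1,000,000 to 6,000 is scored the same as one who stays at 1,000,000: both are positive. The pre-scrub level, which could sharpen the comparison, is used only to check balance.

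The trial is small, and Methods concedes that "there may not be enough subjects recruited for each arm of the study to find a detectable and significant difference". A plan in that position has reason to use the information it collects. As written, the likely result is a set of non-significant positivity comparisons with no planned estimate of the quantity the trial set out to study.

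**Working it through.** **Inputs.** From the documents: four arms, about 15 per arm; cut at 5000 colonies/mL; three Fisher comparisons with povidone-iodine at each of two swabs. Not in the documents, so assumed: two-sided 0.05 per test, normal log counts with equal SD, a true difference of 1 SD, 50% positivity on povidone-iodine, pre/post correlation r of 0.3 to 0.5, and the share of values at a counting limit. No inputs are given for the figure of 15 per arm, so there is no sample-size calculation to reproduce.

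**(a) Loss from dichotomising, seen through the planned test.**
- With 50% positive on povidone-iodine, a 1 SD benefit gives positivity Φ(0 − 1) = 15.9% on the comparator. Enumerating all 16 × 16 tables for 15 v 15, Fisher's power is 34.6%. A 1 SD harm gives the same figure by symmetry. For a benefit, with povidone-iodine positivity of 30-80%, the range is 23-39%.
- Rank-sum test on the counts, simulated: about 71%.
- Unadjusted log-count contrast in a four-arm model: noncentrality = 1 × √(15/2) = 2.739 on 60 − 4 = 56 df; critical t = 2.003; power 77%.
- With baseline adjustment the noncentrality is divided by √(1 − r²). At r = 0.3 it is 2.871 and power is about 80%; at r = 0.5 it is 3.162 and power is about 87%.

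**(b) Loss from Fisher's conservatism.**
- Exact size at nominal 5%: 1.67%, 1.70%, 1.61% and 1.65% at 20%, 30%, 40% and 50% positivity. The tests are valid but well below nominal.
- 4/15 v 0/15: p = 2 × C(15,4)/C(30,4) = 2 × 1365/27405 = 0.0996. By symmetry 11/15 v 15/15 also gives 0.0996. Under Fisher, with 4 or fewer povidone-iodine positives no scrub can be shown better, and with 11 or more none can be shown worse.
- Boschloo's exact test on the same two tables gives p = 0.043. These limits therefore belong to the test, not to the binary endpoint.
- In the 50% v 15.9% case Boschloo has about 49% power against Fisher's 35%. So about 49 − 35 = 14 of the 77 − 35 = 42 points between Fisher and the unadjusted log contrast come from the choice of test; the other 28 come from the cut.

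**Where the gain is smaller.**
- Multiplicity: three unadjusted log-count contrasts against a shared control have a familywise error of about 12%, against 4-5% for three Fisher tests. At 0.05/3 the critical t is 2.468 and the unadjusted log contrast has 61% power, not 77%.
- Values at a lower limit, 1 SD benefit: with 40% of povidone-iodine values at the limit, rank-sum has 59% against Fisher's 35%; with 60% there and the cut just above the limit, 47% against 31%.

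**The case against.** The strongest reply is that the planned analysis is sound and that the quantified gain rests on invented inputs. Much of this stands. Randomisation keeps each Fisher comparison valid, and ignoring the pre-scrub count costs precision without causing bias. The documents give no SD, correlation, positivity rate or counting limit, so every power figure is conditional.

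Four stronger readings are tempting, and the documents do not support them.
- A reader might infer that the tests are biased or invalid. They are conservative, which is the opposite fault.
- A reader might infer that the trial could not report the size of the reduction. Raw counts are to be collected and nothing bars describing them; the supportable statement is that no such analysis is planned.
- A reader might attribute the 4/15 and 11/15 limits to the cut at 5000. They come from Fisher's discreteness.
- A reader might infer that any count-based model wins by a fixed margin. It does not. With 40% of povidone-iodine values at a lower limit, log ANCOVA has only 34-41% power for a scrub 1 SD better (Fisher 34-35%), and its estimate shrinks from 1.0 to 0.4 SD. At 1.5 SD it falls below Fisher (49-56% v 67-68%). The rank-sum test stays ahead there, but its lead depends on where the limit and the cut lie.

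What remains is the mismatch itself, which follows from the Summary and the SAP without any assumption.

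**Conclusion.** The concern holds as a mismatch between question and analysis with a loss of efficiency, and is best treated as a cheap improvement that should be made. Confidence is high that no planned analysis addresses the size of the reduction. It is lower for the amount of power recovered. Under the assumptions stated, power for a 1 SD difference roughly doubles without a multiplicity correction (35% to 71-77%, or 80-87% with baseline adjustment). With an allowance for three contrasts it is 61% unadjusted, and the gain narrows further if many counts sit at a limit. About a third of the 42-point gap to the unadjusted log contrast (14/42) could be recovered by changing the test alone; the rest, and any estimate of magnitude, needs the counts.

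**What to change.** 1. Make the main analysis a four-arm ANCOVA of post-scrub log10 count on arm and pre-scrub log10 count, with three contrasts against povidone-iodine reported as mean log10 differences with 95% CI.
2. Name in advance which count is main (aerobic, anaerobic or fungal, or how they combine). Make the post-scrub swab main and the post-procedure swab secondary. State the alpha and a rule for the three contrasts, for example Dunnett or Holm.
3. Before any count is seen, confirm with the laboratory that numeric counts are reported, and fix the lower and upper counting limits and the value assigned at each.
4. Pre-state pairwise rank-sum tests against povidone-iodine as a sensitivity analysis, or as the main analysis if the laboratory expects many values at the lower limit. Do not make that choice on trial data.
5. With values at a limit, do not present Hodges-Lehmann shifts as the size of the reduction. With 40% of povidone-iodine values at the limit, a true shift of −1 SD is estimated on average as −0.21 SD. Report instead the probability that a povidone-iodine patient has the higher count, with CI, or a censored-model difference using a t reference.
6. Keep the proportion at or above 5000 as a secondary endpoint, with risk differences and CI.

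The cost is SAP wording, short code and a laboratory check, with no new swabs or patients. The downside is a distributional and non-detect assumption: with many values at the lower limit, log ANCOVA understates a better scrub, which is why item 4 must be written in beforehand.

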This study will use block randomization. There will be four arms of the study one for each of the four surgical scrubs. There will be approximately 15 patients per arm. Patients undergoing surgeries which require a vaginal antiseptic preparation will be recruited from Wright State Physicians Obstetrics and Gynecology as well as other participating groups at Miami Valley Hospital. Procedures included in the study are procedures in which a vaginal preparation is performed, including procedures with a vaginal incision (hysterectomy, incontinence procedures), as well as general laparoscopic procedures (diagnostic laparoscopy, salpingectomy, oophorectomy, etc). Procedures excluded from the study are procedures which involve: any local infectious process such as cellulitis or abscess, have significant risk of washout of the vaginal preparation (hysteroscopy or vaginoscopy), any procedures for invasive cancer diagnoses, or procedures with significant risk of bleeding such as dilation and curettage (both for sampling or pregnancy-related), or endometrial ablation. Revision surgeries will also be excluded to decrease any complications. Patients who consent to the study will be given a ID and

will be randomly assigned to one of the four arms. Patients will be excluded if an allergy to any of the scrubs is listed or found. Each recruited patient will be over the age of 18 with ability to consent on their own.

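### The between-arm Fisher tests ignore the pre-scrub result, which costs precision and leaves chance imbalance uncorrected if some women start below 5000

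*Combined protocol and SAP*

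**What the plan says.** In Methods, each patient has a swab before the scrub: "After prophylaxis administration and before surgical antiseptic preparation, a 10 second swab will be taken of the vagina". The Statistical Analysis Plan reduces results to two classes: "Bacterial and fungal colony counts will be coded as positive if counts are ≥ 5000 colonies/mL", otherwise negative. It then uses the pre-scrub class once, in a chi-square comparison of the arms "for colony counts (positive vs negative) at the pre-scrub sample collection". No later step depends on that comparison, and no action is stated if it shows a difference.

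For efficacy, each of the three other scrubs "will be compared to povidone-iodine as the standard of care using Fisher's Exact tests for each pair comparison at the" post-scrub and post-procedure collections. No stratification, adjustment, change from baseline or restriction to women who start positive is stated.

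Entry is by type of operation: "Procedures included in the study are procedures in which a vaginal preparation is performed". No pre-scrub count is required. Randomization is in blocks, with no stratification by pre-scrub result stated, and "There will be approximately 15 patients per arm". The Summary states the expectation as a change from the first swab: "We expect that there will be reduced colony counts at the pre-procedure point with baby shampoo having the least reduction".

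**The concern.** A woman who is negative after the scrub may have been cleared by it, or may have been negative from the start. The planned tests count both alike. Post-scrub status is relevant in itself, because it shows how contaminated the field is, but it is not the reduction that the Summary talks about.

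If some women start below 5000, two things follow:

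- **Dilution.** Women with nothing to clear shrink the difference between scrubs and lower power.
- **Chance imbalance.** With 15 per arm, one arm can easily receive several more baseline-negative women than another. That moves the observed difference even when the scrubs are equal, and the planned analysis does not correct for it.

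If every woman starts at or above 5000, neither arises on this positive/negative scale.

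**Working it through.** **Inputs.** From the documents: 15 women per arm, four arms, a cut at 5000 colonies/mL, and Fisher tests of three scrubs against povidone-iodine. The documents give no significance level, power, effect size or share starting below 5000, so there is no power figure of theirs to reproduce. Assumed:

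- two-sided 5% level;
- *q*, the share starting negative: 0, 10, 20 or 40%;
- *c*, the clearance among women who start positive;
- *k*, the probability that a baseline-negative woman stays negative.

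**Dilution.** The post-scrub positive rate is (1 − q)(1 − c) + q(1 − k). With c = 30% v 80%, q = 20% and k = 1, the rates are 0.8 × 0.7 = 0.56 and 0.8 × 0.2 = 0.16. A 50-point difference in clearance becomes 40 points.

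**Power.** All outcomes were enumerated for two arms of 15. The stratified test combines the hypergeometric distributions of the two pre-scrub strata. With 30% v 80% and k = 1:

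| q | Exact: planned → stratified | Mid-p: planned → stratified | Mid-p gain |
|---|---|---|---|
| 0 | 0.680 → 0.680 | 0.807 → 0.807 | 0 |
| 10% | 0.571 → 0.687 | 0.714 → 0.765 | 0.051 |
| 20% | 0.469 → 0.644 | 0.615 → 0.692 | 0.077 |
| 40% | 0.303 → 0.466 | 0.435 → 0.558 | 0.123 |

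The exact gains are 0.116, 0.175 and 0.163. They overstate what the baseline contributes, because stratifying also makes the exact test less conservative. The mid-p versions have similar size (4–5%), so their gain is the fairer measure. It is under half of the exact gain at 10–20% negative and about three quarters at 40%.

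Other scenarios, for q = 10/20/40%:

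- 30% v 80%, k = 0.9: mid-p gain 0.044/0.060/0.073.
- 30% v 80%, k = 0.7 (more plausible after the procedure): mid-p gain 0.031/0.034/0.030.
- 50% v 80%, k = 1: exact 0.207/0.174/0.116 → 0.282/0.254/0.171; mid-p gain about 0.03 throughout.

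**Size.** With equal scrubs (55% cleared, k = 1), the planned test rejects in 1.6–1.7% of trials and the exact stratified test in 2.6–3.1%. Both are valid.

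**Imbalance.** With two independent binomial counts from 15 women, the chance of a gap of four or more baseline-negative women is 0.033/0.107/0.191 at q = 10/20/40%. The chance that at least one of the three comparisons sharing the povidone-iodine arm has such a gap is 0.080/0.250/0.416.

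When baseline-negative women stay negative, a four-woman gap alone moves the difference in positivity by 4/15 × (1 − c):

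- c = 30%: 0.267 × 0.70 = 0.187
- c = 55%: 0.267 × 0.45 = 0.120
- c = 80%: 0.267 × 0.20 = 0.053

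**Would the baseline test flag it?** Take baseline-negative counts of 1, 5, 3 and 3. The expected counts are 3 negative and 12 positive per arm, so chi-square = (4 + 4)/3 + (4 + 4)/12 = 3.33 on 3 df, p = 0.34. For 2, 6, 4, 4 it is 8/4 + 8/11 = 2.73, p = 0.44. For 4, 8, 6, 6 it is 8/6 + 8/9 = 2.22, p = 0.53. None would be flagged.

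**False positives given a gap of four or more** (exact tests, k = 1). At 55% clearance the planned test rejects in 4–5% of such trials, and the stratified test in about 3%. At 20% clearance the planned test rejects in about 8–10% and the stratified test in about 1.7%. Averaged over all randomizations, the planned test keeps its level.

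**The case against.** The planned analysis is not wrong. An unadjusted Fisher test in a randomized comparison holds its level, and post-scrub status is a legitimate endpoint. The whole loss depends on a share that the documents do not give. The larger power gains need a 50-point difference in clearance and baseline-negative women who mostly stay negative; elsewhere the gain is about 3 points, and with 50% v 80% power stays below 30% by either exact test. The plan already admits that the trial may be too small. If pre-scrub status predicted nothing, the stratified mid-p test would lose slightly (0.807 → 0.800 at 20% negative).

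Most of this stands, and it limits the point to precision and the realised estimate. It does not remove it. The loss when baseline is uninformative is under one point. When no woman starts negative, the stratified test is the planned Fisher test. Randomization protects the average over trials, but it does not correct an imbalance in the one trial that is run. Two further objections bear on the remedy: the organism class that defines the stratum must be stated, and stratifying at the same cut does not turn the outcome into a reduction in counts.

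**Conclusion.** The concern holds. The pre-scrub result is collected from every woman and has no part in the treatment comparisons. If some women start below 5000, the plan loses a modest amount of power: about 5–12 points at similar size in the favourable case (30% v 80% clearance, 10–40% starting negative and staying negative), and about 3 points with weaker effects or less stable baseline-negatives. It also leaves the estimate open to shifts of 5–19 points from a four-woman gap, which at least one comparison would have in 8–42% of trials and which the baseline chi-square would be unlikely to flag. If all women start at or above 5000, there is no loss on this scale. Overall type I error is not at issue. All rates and the 5% level are assumptions, so confidence in the size is medium; confidence in the reading of the plan is high. The change should be made.

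**What to change.** In the Statistical Analysis Plan:

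- Replace each pairwise Fisher test with an exact test stratified by pre-scrub status (at or above 5000 v below), at both collections. Define the stratum by the pre-scrub result for the same organism class as the outcome.
- Report the Mantel-Haenszel risk difference across the two strata with each test.
- State that this applies whatever the baseline comparison shows.
- Add an analysis of women at or above 5000 pre-scrub, labelled as supporting. The swab precedes the scrub, so this restriction keeps the randomized comparison and addresses clearance directly.

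The cost is SAP wording. The swab is already taken and cultured, and no further patients, samples or clinical changes are needed.
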